8.2.3. Clinical Safety Laboratory Assessments

Clinical safety laboratory tests are not required by this protocol.

If laboratory values from non-protocol-specified laboratory assessments performed at the institution's local laboratory require a change in participant management or are considered clinically significant by the investigator (eg, SAE or AE or dose modification), then the results must be recorded in the CRF.

8.3. Adverse Events and Serious Adverse Events

The definitions of an AE and an SAE can be found in [Appendix 3](#).

AEs will be reported by the participant's parent(s)/legal guardian(s). Events that, in the clinical judgment of the investigator, are 1) consistent with normal growth and development and 2) do not differ significantly in frequency or severity from expected are not generally to be considered AEs. Examples may include, but are not limited to, teething, contact diaper rash, spitting up, colic, or typical fussiness/crying in infants and children.

The investigator and any qualified designees are responsible for detecting, documenting, and recording events that meet the definition of an AE or SAE and remain responsible to pursue and obtain adequate information both to determine the outcome and to assess whether it meets the criteria for classification as an SAE or caused the participant to discontinue from the study (see [Section 7](#)).

In addition, the investigator may be requested by Pfizer Safety to obtain specific follow-up information in an expedited fashion.

8.3.1. Time Period and Frequency for Collecting AE and SAE Information

The time period for actively eliciting and collecting AEs and SAEs ("active collection period") for each participant begins from the time the participant's parent(s)/legal guardian(s) provides informed consent, which is obtained before the participant's participation in the study (ie, before undergoing any study-related procedure and/or receiving investigational product), through and including Visit 3, and from Visit 4 through Visit 5. SAEs and NDCMCs will be recorded and reported from the signing of the ICD through the final visit (Visit 5). At Visit 5, the participant's parent(s)/legal guardian(s) will be asked to report any AEs and SAEs, including hospitalizations and NDCMCs, that have occurred since Visit 4.

Follow-up by the investigator continues throughout and after the active collection period and until the event or its sequelae resolve or stabilize at a level acceptable to the investigator, and Pfizer concurs with that assessment.

Investigators are not obligated to actively seek AEs or SAEs after conclusion of the study participation. However, if the investigator learns of any SAE, including a death, at any time after a participant has completed or withdrawn early from the study, and he/she considers the event to be reasonably related to the study intervention or study participation, the investigator must promptly notify the sponsor.

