To describe the safety profile of 20vPnC	
In participants receiving at least 1 dose of investigational product and having safety data reported after any vaccination in each vaccine group:
 
 • The percentage of participants reporting prompted local reactions within 7 days after each vaccination • The percentage of participants reporting prompted systemic events within 7 days after each vaccination • The percentage of participants reporting AEs from Dose 1 to 1 month after Dose 2 and from Dose 3 to 1 month after Dose 3 • The percentage of participants reporting SAEs through 1 month after Dose 3 	
 • Prompted local reactions (redness, swelling, and pain at the injection site) • Prompted systemic events (fever, decreased appetite, drowsiness/increased sleep, and irritability) • AEs • SAEs • NDCMCs

	
 The percentage of participants reporting NDCMCs through 1 month after Dose 3 	
Primary Pneumococcal Immunogenicity Objectives	Estimands	Primary Pneumococcal Immunogenicity Endpoints
To demonstrate that the percentages of participants with predefined serotype-specific IgG concentrations for the 13 serotypes in the 20vPnC group are noninferior to those of the corresponding serotypes in the 13vPnC group at 1 month after Dose 2	
In evaluable participants at 1 month after Dose 2:
 
 For each of the 13 matched serotypes: difference in the percentages of participants with predefined IgG concentrations between the 20vPnC group and the 13vPnC group 	
 Pneumococcal IgG concentrations
To demonstrate that the percentages of participants with predefined serotype-specific IgG concentrations for the 7 additional serotypes in the 20vPnC group are noninferior to the lowest among the 13 serotypes in the 13vPnC group at 1 month after Dose 2	
In evaluable participants at 1 month after Dose 2:
 
 For each of the 7 additional serotypes in 20vPnC: difference in the percentages of participants with predefined IgG concentrations between the 20vPnC group and the lowest percentage of participants with predefined IgG concentrations among the 13 serotypes from the 13vPnC group 	
 Pneumococcal IgG concentrations

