8.2. Safety Assessments

Planned time points for all safety assessments are provided in the [SoA](#). Unscheduled clinical laboratory measurements may be obtained at any time during the study to assess any perceived safety concerns.

A clinical assessment, including medical history and measurement of temperature, will be performed on all participants prior to vaccination to determine participant eligibility and to establish a clinical baseline. Significant medical history and significant findings from any physical examination (if performed) will be recorded as medical history on the CRF. Temperature measurement prior to vaccination will be documented and recorded on the CRF.

The participant will be observed for 30 minutes after each study vaccination and any reactions occurring during that time will be recorded as AEs.

Local reactions (including redness, pain, and swelling at the injection site), systemic events (including fever, drowsiness/increased sleep, decreased appetite, and irritability), and use of pain/fever medication will be prompted for and collected by the participant's parent(s)/legal guardian(s) daily for 7 days after each study vaccination (where Day 1 is the day of vaccination) in an e-diary. These prompted e-diary events are graded as described in Section 8.2. AEs, SAEs, and NDCMCs will be collected as defined in [Section 8.3](#).

AEs will be recorded and reported from the signing of the ICD through Visit 3 and from Visit 4 through Visit 5.

SAEs and NDCMCs will be recorded and reported from the signing of the ICD through the final visit (Visit 5).

Causality and severity of AEs and SAEs will be assessed for all participants.

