8.3.1.1. Reporting SAEs to Pfizer Safety

All SAEs occurring in a participant during the active collection period are reported to Pfizer Safety on the Vaccine SAE Reporting Form immediately upon awareness and under no circumstance should this exceed 24 hours, as indicated in [Appendix 3](#). The investigator will submit any updated SAE data to the sponsor within 24 hours of it being available.

SAEs occurring in a participant after the active collection period has ended are reported to Pfizer Safety if the investigator becomes aware of them; at a minimum, all SAEs that the investigator believes have at least a reasonable possibility of being related to investigational product must be reported to Pfizer Safety.

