8.3.1.2. Recording Nonserious AEs and SAEs on the CRF

During the active collection period, both nonserious AEs and SAEs are recorded on the CRF.

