8.10.4. Visit 4 (Dose 3: 335 to 386 Days of Age)

- Ensure and document that the participant continues to be eligible for the study (see [Section 7](#) for participant discontinuation/withdrawal) and none of the temporary delay criteria are met ([Section 5.5](#)).
- Confirm whether the parent(s)/legal guardian(s) still possesses the participant contact card.
- Record nonstudy vaccinations administered since Visit 3, as described in [Section 6.5.4](#).
- Determine whether any SAEs or NDCMCs have occurred since the previous visit and follow up on any previously reported events to determine the outcome (ie, record stop dates or confirm if they are still continuing) and record as described in [Section 10.3.4](#), and record concomitant medications used to treat NDCMCs and SAEs. Any AEs that have occurred since the last visit will be documented in the participant's source documents; however, they will not be captured on the CRF.
- Measure and record the participant's temperature (°C).
- Collect a blood sample of approximately 5 mL for immunogenicity (a topical anesthetic is permitted).
- Administer a single 0.5-mL injection of 20vPnC or 13vPnC into the left anterolateral thigh.
- Administer concomitant vaccine containing DTaP, HBV, IPV, and Hib antigens and other permitted vaccines. These vaccines must be given in a limb other than the site of

20vPnC or 13vPnC administration, as appropriate for the age of the child and the route of administration (ie, intramuscular, subcutaneous, or oral). The sites of administration will be captured on the CRF.

- MMR and varicella vaccines are intended to be given to all participants. However, in case of circumstances due to local practice/recommendations, some sites may not administer them to their participants, in which case MMR and varicella vaccines will be considered nonstudy vaccines. These vaccinations must be given in a limb other than the site of administration of 20vPnC or 13vPnC, as appropriate for the age of the child and the route of administration (ie, intramuscular or subcutaneous). The sites of administration will be captured on the CRF.

After vaccination:

- Site staff will observe the participant for 30 minutes after vaccination for any reactions. Record any AEs on the CRF and on an SAE form as applicable. Record concomitant medications used to treat SAEs and NDCMCs.

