10.3.4. Recording/Reporting and Follow-up of AEs and/or SAEs

AE and SAE Recording/Reporting

The table below summarizes the requirements for recording adverse events on the CRF and for reporting serious adverse events on the Vaccine SAE Reporting Form to Pfizer Safety. These requirements are delineated for 3 types of events: (1) SAEs; (2) nonserious AEs; and (3) exposure to the investigational product under study during pregnancy or breastfeeding, and occupational exposure.

It should be noted that the Vaccine SAE Reporting Form for reporting of SAE information is not the same as the AE page of the CRF. When the same data are collected, the forms must be completed in a consistent manner. AEs should be recorded using concise medical terminology and the same AE term should be used on both the CRF and the Vaccine SAE Reporting Form for reporting of SAE information.

Safety Event	Recorded on the CRF	Reported on the Vaccine SAE Reporting Form to Pfizer Safety Within 24 Hours of Awareness
SAE	All	All
Nonserious AE	All	None
Exposure to the investigational product under study during pregnancy or breastfeeding, and occupational exposure	None	All (and exposure during pregnancy [EDP] supplemental form for EDP)

- When an AE/SAE occurs, it is the responsibility of the investigator to review all documentation (eg, hospital progress notes, laboratory reports, and diagnostic reports) related to the event.
- The investigator will then record all relevant AE/SAE information in the CRF.
- It is **not** acceptable for the investigator to send photocopies of the participant's medical records to Pfizer Safety in lieu of completion of the Vaccine SAE Reporting Form/AE/SAE CRF page.
- There may be instances when copies of medical records for certain cases are requested by Pfizer Safety. In this case, all participant identifiers, with the exception of the participant number, will be redacted on the copies of the medical records before submission to Pfizer Safety.
- The investigator will attempt to establish a diagnosis of the event based on signs, symptoms, and/or other clinical information. Whenever possible, the diagnosis (not the individual signs/symptoms) will be documented as the AE/SAE.

Assessment of Intensity		

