6.1.1.4. Serious Adverse Events and Newly Diagnosed Chronic Medical Conditions

6.1.1.4.1. Main Analyses

- Estimands:
 - The percentage of participants reporting SAEs from Dose 1 to 1 month after Dose 3 ([Section 2.1](#)).
 - The percentage of participants reporting NDCMCs from Dose 1 to 1 month after Dose 3 ([Section 2.1](#)).
- Analysis set: Safety population ([Section 4](#)).
- Analysis time point: Dose 1 to 1 month after Dose 3.
- Analysis methodology: For percentages, the 2-sided Clopper-Pearson CIs will be calculated for each vaccine group ([Section 5.2.1](#)).
- Intercurrent events and missing data: No missing values will be imputed except for partial SAE/NDCMC start dates ([Section 5.3](#)).
- Reporting results: The numerator (n) and the denominator (N) used in the percentage calculation, the percentage (%), and the corresponding 2-sided Clopper-Pearson 95% CI for participants reporting any SAEs/NDCMCs, by each SOC, and each preferred term within SOCs will be presented by vaccine group. SAEs and NDCMCs will be presented separately.

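### Does the interrupted active collection period in Protocol 8.3.1 leave serious adverse events between Visit 3 and Visit 4 outside recording and 24-hour reporting?

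*Protocol*

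**What the plan says.** Protocol 8.3.1 sets a single active collection period, named for AEs and SAEs together. It starts at consent and runs "through and including Visit 3, and from Visit 4 through Visit 5". Two subsections build on that term. Section 8.3.1.1 says "All SAEs occurring in a participant during the active collection period are reported to Pfizer Safety", with an outer limit of 24 hours, and refers to Appendix 3. Section 8.3.1.2 says "During the active collection period, both nonserious AEs and SAEs are recorded on the CRF".

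Other places give SAEs and newly diagnosed chronic medical conditions (NDCMCs) a period with no break:

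- The sentence that follows the definition in 8.3.1, and Section 8.2 in the same words: "SAEs and NDCMCs will be recorded and reported from the signing of the ICD through the final visit (Visit 5").
- The synopsis, which collects both from consent to 1 month after Dose 3.
- The Visit 4 procedures (8.10.4): "Determine whether any SAEs or NDCMCs have occurred since the previous visit", to be recorded as described in 10.3.4.
- The table in 10.3.4 (Appendix 3), which has one column for CRF entry and one headed "Reported on the Vaccine SAE Reporting Form to Pfizer Safety Within 24 Hours of Awareness". The SAE row reads All in both, with no period attached.
- The primary safety estimand: "The percentage of participants reporting SAEs through 1 month after Dose 3". SAP 6.1.1.4.1 analyses "The percentage of participants reporting SAEs from Dose 1 to 1 month after Dose 3", and SAP 2.2 and 3.1.1.5 describe collection over the whole study.

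**The concern.** A defined term normally controls the rules that use it. Here the term covers SAEs by name and stops between Visit 3 and Visit 4, and both the expedited report and the CRF entry depend on it. The other rule in 8.3.1.1, for SAEs after the period is over, is weaker: it depends on the investigator becoming aware, makes related events the minimum, and repeats no 24-hour limit. A site that read only these subsections might report an interval SAE late, or apply the weaker rule to it.

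The interval is the longest between any two visits, and SAEs are a primary safety endpoint. If interval SAEs were missed, the percentage reported through 1 month after Dose 3 would be too low. If sites read the text differently, expedited reporting would be uneven.

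**Working it through.** The plan gives no figure to reproduce. The check has two parts: how long the interval is, and what each section requires within it.

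**Length of the interval.** The windows come from the schedule of activities (Protocol 1.3):

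- age at Visit 1: a1 = 42 to 112 days
- Visit 1 to Visit 2: d2 = 42 to 63 days
- Visit 2 to Visit 3: d3 = 28 to 42 days
- age at Visit 4: a4 = 335 to 386 days
- Visit 4 to Visit 5: d5 = 28 to 42 days

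Gap from Visit 3 to Visit 4 = a4 − a1 − d2 − d3. Follow-up from Visit 1 to Visit 5 = a4 − a1 + d5.

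- Smallest share: gap 335 − 112 − 63 − 42 = 118 days; follow-up 335 − 112 + 42 = 265 days; 118/265 = 44.5%.
- Largest share: gap 386 − 42 − 42 − 28 = 274 days; follow-up 386 − 42 + 28 = 372 days; 274/372 = 73.7%.
- Window midpoints: gap 360.5 − 77 − 52.5 − 35 = 196 days; follow-up 360.5 − 77 + 35 = 318.5 days; 196/318.5 = 61.5%.

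**What applies to an SAE in that interval.**

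| Place | Requirement in the interval |
|---|---|
| 8.3.1, definition | Outside the named period |
| 8.3.1.1 and 8.3.1.2 | Duties stated for SAEs inside the period; no prohibition outside it |
| 8.3.1, next sentence, and 8.2 | Record and report, consent to Visit 5 |
| 8.10.4 | Ask at Visit 4 about SAEs since Visit 3; record under 10.3.4 |
| 10.3.4 table | All SAEs on the CRF; all SAEs reported within 24 hours of awareness |
| SAP 2.2 and 3.1.1.5 | Collected throughout the study |

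The first two rows fail to impose a duty; the others impose one. A site can comply with all of them at once, and when it does, an interval SAE is entered on the CRF and reported within 24 hours of awareness. The 24-hour rule also has a basis outside the defined term, because 8.3.1.1 points to Appendix 3.

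The weaker rule fits the interval poorly. It addresses a period that has ended, and 8.3.1 releases investigators from active follow-up only once study participation is over. Between Visit 3 and Visit 4 the infant is still in the study. Even if the weaker rule were applied, it sets a floor and leaves the stricter rules in force.

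The separation of event types is explicit at Visit 4. The bullet in 8.10.4 that sends interval SAEs to the CRF keeps interval AEs in source documents only. Awareness need not wait for Visit 4 either: under 8.10.2 and 8.10.6, parents are told to contact the site about significant illness or hospitalization during the study.

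**The case for a change.** The best case for a change is that no single meaning of the term suits every section that touches it. If the period is interrupted, 8.3.1.1 and 8.3.1.2 omit interval SAEs. If it is continuous, 8.3.1.2 would put interval nonserious AEs on the CRF, which 8.10.4 rules out. One label is doing two jobs, in the subsections that set an absolute reporting limit, and separate periods would take only a few words. The Appendix 3 table cannot settle the period alone, since it also reads All for nonserious AEs on the CRF.

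The drafting criticism stands. The practical consequence does not follow. Under the interrupted reading the two subsections are silent on interval SAEs, and that silence is filled by the next sentence of the same section, by 8.2 and by the Visit 4 procedures. The table is supporting evidence, made operative for interval SAEs by the reference in 8.10.4.

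Two qualifications apply to the continuous rule. The SAE/NDCMC row of the primary schedule of activities appears split in the extracted text, like the AE row. The table may have been broken in extraction, and the Russian cohort's row appears as one bar, so the split is weak evidence either way. Separately, 7.1, 7.2 and a schedule footnote set a 1-month safety follow-up after the last vaccination for infants who stop vaccination or withdraw. That is a rule for a different situation.

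**Conclusion.** The concern does not call for a change. Protocol 8.3.1 puts two event types under one label and leaves a break that is meant only for nonserious AEs. This is a slip in drafting. The operative rule for SAEs is continuous recording and reporting from consent to Visit 5, and it is stated in the same section and repeated where sites act on it.

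The effect on the primary safety estimand, the analysis sets, power and type I error is nil. The 118 to 274 days (44.5% to 73.7% of follow-up) give the length of the Visit 3 to Visit 4 interval. The documents offer no basis for estimating any number of late reports. The conclusion assumes that sites read 8.3.1 to the end and carry out the Visit 4 procedures as written. Separate wording for the two periods would read better, but it would alter no duty, data item or result.

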8.3.1.1. Reporting SAEs to Pfizer Safety

All SAEs occurring in a participant during the active collection period are reported to Pfizer Safety on the Vaccine SAE Reporting Form immediately upon awareness and under no circumstance should this exceed 24 hours, as indicated in [Appendix 3](#). The investigator will submit any updated SAE data to the sponsor within 24 hours of it being available.

SAEs occurring in a participant after the active collection period has ended are reported to Pfizer Safety if the investigator becomes aware of them; at a minimum, all SAEs that the investigator believes have at least a reasonable possibility of being related to investigational product must be reported to Pfizer Safety.

8.3.1.2. Recording Nonserious AEs and SAEs on the CRF

During the active collection period, both nonserious AEs and SAEs are recorded on the CRF.

8.3.2. Method of Detecting AEs and SAEs

The method of recording, evaluating, and assessing causality of AEs and SAEs and the procedures for completing and transmitting SAE reports are provided in [Appendix 3](#).

Care will be taken not to introduce bias when detecting AEs and/or SAEs. Open-ended and nonleading verbal questioning of the participant's parent(s)/legal guardian(s) is the preferred method to inquire about AE occurrences.

8.3.3. Follow-up of AEs and SAEs

After the initial AE/SAE report, the investigator is required to proactively follow each participant at subsequent visits/contacts. For each event, the investigator must pursue and obtain adequate information until resolution, stabilization, the event is otherwise explained, or the participant is lost to follow-up (as defined in [Section 7.3](#)).

In general, follow-up information will include a description of the event in sufficient detail to allow for a complete medical assessment of the case and independent determination of possible causality. Any information relevant to the event, such as concomitant medications and illnesses, must be provided. In the case of a participant death, a summary of available autopsy findings must be submitted as soon as possible to Pfizer Safety.

Further information on follow-up procedures is given in [Appendix 3](#).

8.3.4. Regulatory Reporting Requirements for SAEs

Prompt notification by the investigator to the sponsor of an SAE is essential so that legal obligations and ethical responsibilities towards the safety of participants and the safety of a study intervention under clinical investigation are met.

The sponsor has a legal responsibility to notify both the local regulatory authority and other regulatory agencies about the safety of a study intervention under clinical investigation. The sponsor will comply with country-specific regulatory requirements relating to safety reporting to the regulatory authority, institutional review boards (IRBs)/ethics committees (ECs), and investigators.

Investigator safety reports must be prepared for suspected unexpected serious adverse reactions (SUSARs) according to local regulatory requirements and sponsor policy and forwarded to investigators as necessary.

An investigator who receives an investigator safety report describing an SAE or other specific safety information (eg, summary or listing of SAEs) from the sponsor will review and then file it along with the IB and will notify the IRB/EC, if appropriate according to local requirements.

